**List of abbreviations**

AE	Adverse Event
AESI	Adverse Event of Special Interest
ALP	Alkaline Phosphatase
ALT	Alanine Aminotransferase
ASCVD	Atherosclerotic Cardiovascular Disease
AST	Aspartate Aminotransferase
ATC	Anatomical Therapeutic Chemical classification system
BMI	Body Mass Index
BUN	Blood Urea Nitrogen
CHD	Coronary Heart Disease
CI	Confidence Interval
CK	Creatine Kinase
CS	Clinically significant
CVD	Cerebrovascular Disease
CRF	Case Report Form
CSR	Clinical Study Report
DBL	Database Lock
EAIR	Exposure-adjusted Incidence Rate
eCRF	Electronic Case Report Form
eGFR	Estimated Glomerular Filtration Rate
EOS	End of Study
GGT	Gamma Glutamyl Transferase
HbA1c	Glycated Hemoglobin A1C
HDL-C	High-density Lipoprotein Cholesterol
HeFH	Heterozygous Familial Hypercholesterolemia
HLGT	High-level Group Term
HLT	High-level Term
hsCRP	High Sensitivity C-reactive Protein
IA	Interim Analyses
LDL-C	Low-density Lipoprotein Cholesterol
LLN	Lower Limit of the Normal range
LLQ	Lower Limit of Quantification
LMT	Lipid Modifying Therapy
MACE	Major Adverse Cardiovascular Event
MedDRA	Medical Dictionary for Drug Regulatory Affairs
PAD	Peripheral Artery Disease
PCS	Potentially Clinically Significant
PPC	Post-Production Change
PT	Preferred Term
SAE	Serious Adverse Event

SAP	Statistical Analysis Plan
SAS	Statistical Analysis System
SC	Subcutaneous
SD	Standard Deviation
SMQ	Standardized MedDRA Query
SOC	System Organ Class
TBIL	Total Bilirubin
TC	Total Cholesterol
TEAE	Treatment Emergent Adverse Event
TESAE	Treatment Emergent Serious Adverse Event
TFLs	Tables, Figures, Listings
ULN	Upper Limit of the Normal range
WHO	World Health Organization

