Subjects moving over from the open-label ORION-3 study will not receive study drug at Day 1. Their first dose of study drug in this trial will be at Day 90. This is to maintain their semi-annual dosing schedule on inclisiran treatment.

After the Day 90 dosing, subjects rolled over from all feeder trials (ORION-3/9/10/11) will return for open-label drug administration of inclisiran sodium 300 mg every 180 days until Day 990. The EOS visit will be on Day 1080. For subjects who discontinued early, the EOS visit should be completed  $\geq 90$  days following the last inclisiran injection whenever possible.

[figure not shown]
The duration that each subject is expected to participate in this study is a maximum of 3 years or the occurrence of one of the following events, whichever occurs first:

- a recommendation of discontinuation by the investigator or Sponsor,
- a decision by the subject to discontinue for any reason,
- an administrative decision is made to end the study. In particular, the decision has been made to end the study after the last subject from ORION-9/10/11 completes the 3-year treatment (or discontinued early). As a result, ORION-3 rollover subjects will have shorter than 3 years of participation in this study.

No formal interim analysis will be performed in this study.

A schematic diagram of the study design is presented in [Figure 1-1](#). Note that the study duration for ORION-3 rollover subjects will be shorter than the three-year duration illustrated in the diagram.

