### 2.1 Data analysis general information

All analyses will be performed by Novartis, [REDACTED]. [REDACTED] The most recent version of SAS available in the statistical programming environment of Novartis will be used for the analysis.

Study-collected data will be summarized by the actual treatment groups of the feeder studies (Phase III Inclisiran-Inclisiran, Phase III Placebo-Inclisiran, ORION-3 Rollover) using descriptive statistics, graphs, and/or raw data listings. Categorical variables will be summarized using counts and percentages. Percentages are based on the number of subjects in the analysis set for whom there are non-missing data, unless otherwise specified. For selected categorical variables, the 95% confidence interval (CI) for the percentage will be calculated using Blaker's method. Continuous variables, including changes from baseline, will be summarized using

descriptive statistics (n (number of non-missing observations), mean, standard deviation (SD), median, first and third quartiles (Q1 and Q3), minimum and maximum). For selected continuous variables, the CI for the mean will be provided.

Absolute change and percent change from baseline will be calculated as follows:

- Absolute change from baseline to Day X = Value at Day X – Baseline value.
- Percent change from baseline to Day X = (Absolute change/Baseline value)\*100%.

For laboratory measurements below the lower limit of quantification (LLQ), LLQ/2 will be used as the numeric value for the measurement. For example, if numeric result is missing in the database and character result is “< 3”, the numeric result should be treated as  $3/2 = 1.5$  during analysis.

Analyses for the final CSR will be conducted after the final database lock (DBL) of the study. The final DBL will be performed after ORION-9/10/11 rollover subjects either complete the Day 1080 visit or discontinue early and will not wait until ORION-3 rollover subjects complete Day 1080 visit. The ORION-3 rollover subjects will have shorter than 3 years of participation in this study, and their EOS visit will be scheduled 90 days after their last dosing visit.

Information regarding DMC analysis will be provided in the DMC charter and a separate DMC SAP/TFL shells.

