### **2.3 Subject disposition, demographics and other baseline characteristics**

#### **2.3.1 Subject disposition**

The following information will be summarized for the Safety Population overall and by treatment group of the feeder studies:

- The number of subjects in each analysis population
- The number of subjects by country and site

- The number of subjects who completed the study and discontinued early, with reasons for discontinuation
- The duration on study (days)
- Protocol deviations and violations of subject restrictions

Completers are defined as subjects indicated in the EOS page of eCRF to have completed the study. This will include ORION-9/10/11 rollover subjects who have completed the Day 1080 visit, and ORION-3 rollover subjects whose study duration is shortened to < 3 years by the administrative decision only.

The duration on study is defined as the number of days from Day 1 of ORION-8 to the date of last recorded contact/participation date in the database.

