## **2.4 Treatments (study treatment, rescue medication, concomitant therapies, compliance)**

### **2.4.1 Study treatment / compliance**

Study drug administration will be summarized for the Safety Population overall and by treatment group of the feeder studies. The summary will include

- The number and percentage of subjects dosed at each visit
- The number and percentage of subjects administered 0, 1, 2, ... doses, and total number of doses administered
- The number and percentage of injections at each injection site location (with total number of administered doses as the denominator for the percentage)
- The number and percentage of injections with each injection volume (with total number of administered doses as the denominator for the percentage)
- The number and percentage of subjects who missed 0, 1, 2, ... doses, and total number of missed doses. As per protocol, ORION-3 rollover subjects do not receive study medication on Day 1, thus ORION-3 rollover subjects who did not receive study medication on Day 1 do not count toward missed doses.

- The number and percentage of missed injections with each reason of not administering study drug (with total number of missed doses as the denominator for the percentage)

The duration of exposure (days) to inclisiran and the total subject-years of exposure in ORION-8 will be summarized for the Safety Population overall and by treatment group of the feeder studies.

The duration of exposure to inclisiran is defined as the number of days from Day 1 of ORION-8 to the earliest of the following:

- Last recorded contact/participation date of ORION-8
- Last study drug administration date in ORION-8 (if any) + 180 days

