### **2.7.1 Adverse events (AEs)**

The most recent version of MedDRA before DBL will be used for coding AEs. An AE will be counted as an ORION-8 treatment emergent AE (TEAE) if the AE started on or after ORION-8 baseline or the AE was present prior to ORION-8 baseline but increased in severity on or after

ORION-8 baseline. Since the investigators are required to enter any worsened AE as a separate record, implementation-wise an AE is a TEAE as long as its onset date/time  $\geq$  date/time of ORION-8 baseline.

The following summaries will be presented for ORION-8 TEAEs using number and percentage of subjects with the event:

- Overall Summary of TEAEs
- TEAEs by primary SOC and PT
- TEAEs by PT
- TEAEs by primary SOC, PT, and maximum severity
- TEAEs possibly related to study drug by primary SOC and PT
- Treatment Emergent Serious AEs (TESAEs) by primary SOC and PT
- TESAEs by PT
- TESAEs possibly related to study drug by primary SOC and PT
- TEAEs leading to withdrawal of study treatment by primary SOC and PT
- TEAEs with a fatal outcome by primary SOC and PT

Subject data listings will be presented for AEs with a fatal outcome, SAEs, and AEs leading to drug discontinuation. Those listings will include all AEs in ORION-8 database, regardless of whether they are ORION-8 TEAE.

If more than one event occurred with the same SOC/PT for the same subject, the subject will be counted only once for that SOC/PT, using the most severe occurrence for the summary by severity.

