#### 2.7.1.1.2 Other AESIs and AEs of additional safety topics

Other AESIs include:

- Hepatic events
- Diabetes mellitus (see [Section 2.7.4](#) for additional analyses for diabetes)

Additional safety topics include:

- Renal events
- Hypersensitivity
- Neurological events and neurocognitive disorders
- Ophthalmological events
- Cardiac safety: Major adverse cardiovascular events (MACE) and each of the MACE components

See [Appendix 5.2](#) for the search criteria of each safety topic.

The following summaries of ORION-8 TEAEs will be presented for other AESIs and AEs of additional safety topics using number and percentage of subjects with the event:

- Overall Summary of TEAEs
- TEAEs by PT

- TEAEs by PT and maximum severity
- TEAEs possibly related to study drug by PT
- TESAEs by PT
- TEAEs leading to study drug withdrawal

Subject data listings will be provided for hepatic and diabetic AEs. Such listings will include all AEs in ORION-8 database, regardless of whether they are ORION-8 TEAE.

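### Adverse event tables use crude subject percentages with no person-time, so at equal risk the administratively shortened ORION-3 column reads lower than the Phase III columns

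*SAP*

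**What the plan says.** For TEAEs, serious TEAEs and fatal TEAEs, SAP 2.7.1 states: "The following summaries will be presented for ORION-8 TEAEs using number and percentage of subjects with the event". SAP 2.7.1.1.1 does the same for injection-site events. SAP 2.7.1.1.2 covers hepatic events, diabetes, the additional safety topics and MACE: "summaries of ORION-8 TEAEs will be presented for other AESIs and AEs of additional safety topics using number and percentage of subjects". Under SAP 2.7 the results appear overall and by feeder group (Phase III Inclisiran-Inclisiran, Phase III Placebo-Inclisiran, ORION-3 Rollover).

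Follow-up is not the same in the three columns. SAP 2.1 ties the final database lock to the Phase III rollovers reaching Day 1080 or stopping early. For the third group, SAP 1.1 says: "As a result, ORION-3 rollover subjects will have shorter than 3 years of participation in this study". SAP 2.1 adds that "their EOS visit will be scheduled 90 days after their last dosing visit".

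Person-time appears in two places. The abbreviation list contains "Exposure-adjusted Incidence Rate", a term the body of the SAP never uses. SAP 2.4.1 says that "total subject-years of exposure in ORION-8 will be summarized for the Safety Population overall and by treatment group", but no adverse event table takes that as a denominator. Two other planned outputs go beyond percentages: the number of injection-site TEAEs per subject (SAP 2.7.1.1.1) and time to new-onset diabetes (SAP 2.7.4.4). Neither adjusts the incidence tables for length of follow-up.

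**The concern.** The proportion of subjects with at least one event grows with time observed. When one of three adjacent columns is stopped early for administrative reasons, its percentages are lower even if the risk per year is identical. Long-term safety is a primary objective, and these are its main tables. A reader comparing columns could take a low ORION-3 figure for serious events or MACE as lower risk in the subjects with the longest prior exposure to inclisiran, when it reflects shorter observation. The disposition table will not warn of this, because SAP 2.3.1 counts ORION-3 subjects shortened only by the administrative decision as completers.

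**Working it through.** The plan states no event rate or ORION-3 follow-up time, so there is no figure of its own to reproduce. What follows is an illustration.

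**Inputs from the documents.** Phase III EOS is Day 1080. Doses are given at Days 90, 270, 450, 630, 810 and 990 (Protocol Table 6-1). With EOS 90 days after the last dose, possible ORION-3 EOS days include 900, 720 and 540. Enrollment closed in February 2020 with 2991 subjects, and ORION-3 was added by Amendment 2 of 06-Oct-2020.

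**Assumptions.** The hazard h is constant and equal in all columns, with a single EOS day per column and no dropout.

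**Step 1: crude percentages.** T = (EOS day − 1)/365.25 and p = 1 − exp(−hT).

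| EOS day | T (years) | h = 1 per 100 | h = 5 per 100 | h = 10 per 100 |
|---|---|---|---|---|
| 1080 (Phase III) | 2.954 | 2.9% | 13.7% | 25.6% |
| 900 | 2.461 | 2.4% | 11.6% | 21.8% |
| 720 | 1.969 | 1.9% | 9.4% | 17.9% |
| 540 | 1.476 | 1.5% | 7.1% | 13.7% |

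Over these rates the ORION-3 column reads about 0.84–0.85, 0.67–0.70 or 0.50–0.54 of the Phase III column. Dropout does not remove the gap. If Phase III would show 10% at 1080 days without dropout, 20% dropout in every column gives 9.0%, against 6.3% at 720 days and 4.9% at 540 days.

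**Step 2: how long ORION-3 follow-up could be.** Assume the last Phase III subject entered by 29-Feb-2020 and ORION-3 entry began on or after 06-Oct-2020. The last Phase III Day 1080 is then 29-Feb-2020 + 1079 days = 12-Feb-2023, which is 859 days after 06-Oct-2020. A Day 810 dose falls 809 days after entry, inside that span. Its EOS 90 days later is at 899 days, 899 − 859 = 40 days past the last Phase III Day 1080. Neither SAP 1.1 nor 2.1 requires ORION-3 EOS to fall by that date, so Day 900 is reachable without visit windows. Later entry gives the shorter cases.

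**Step 3: overall column.** Shift = ORION-3 share × gap. At h = 10 per 100 the gaps are 3.8, 7.7 and 11.9 points for Day 900, 720 and 540. Taking 3300 − 2991 = 309 as an illustrative group size, the share is 309/3300 = 9.4% and the shift is 0.4, 0.7 and 1.1 points. With 150 of 3141 the range is 0.2 to 0.6; with 400 of 3391 it is 0.4 to 1.4.

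**Step 4: can a reader divide by the SAP 2.4.1 subject-years?** That exposure does not stop at the first event, so the quotient is p/T.

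- True 10 per 100: 8.7 (Phase III) against 8.9, 9.1 and 9.3. This is usable.
- True 60 per 100, a common event: 28.1 (Phase III) against 31.3, 35.2 and 39.8. The shorter column now looks worse.

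**Step 5: first-event rate.** Expected time at risk per subject is (1 − exp(−hT))/h. Dividing p by it returns h, so every column shows 10 per 100 (or 60) whatever the EOS day.

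**The case against.** The strongest reply is that the study is declared noncomparative and its safety analysis descriptive. Protocol 10.3.4.1 itself prescribes number and percentage, no test or decision sets ORION-3 against the other columns, and the shorter follow-up is openly stated. Duration on study and subject-years are planned by group, and for uncommon events a reader can divide by them. All of this stands, and it limits the consequence to how one column is read. It does not remove the artefact, and the division fails for common events and yields no CI.

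Several stronger readings are tempting but unsupported:

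- **Percentages are the only planned measure.** They are not, given the injection-site counts and time to new-onset diabetes.
- **ORION-3 follow-up is capped at 859 days.** Step 2 shows the documents impose no such cap. At Day 900 the gap is modest: 3.8 points at 10 per 100, against a 95% half-width of 1.96 × √(0.218 × 0.782/309) = 4.6 points if the group numbers 309.
- **The abbreviation entry proves that a rate analysis was dropped.** That list also carries interim analyses, though none is planned, so it may be template residue.
- **The 2.4.1 cap, "Last study drug administration date in ORION-8 (if any) + 180 days", is a serious flaw.** It rarely binds for completers, whose EOS is about 90 days after the last dose. The material problem is that exposure runs on past the first event.

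**Conclusion.** The point holds. At equal risk and with similar early discontinuation, the ORION-3 column is expected to read lower in every crude incidence table, purely from planned follow-up. That direction follows from the SAP's own text.

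The size rests on ORION-3 follow-up, group size and event rates that the documents do not give. On the assumptions above it runs from a modest shortfall at Day 900 (about 0.85 of the Phase III figure) to about half at Day 540. The 309 is an approximate target minus an enrollment count and is not an estimate of the group.

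A reader might infer that the trial's safety conclusions as a whole are compromised. The documents do not support that. The two Phase III columns share the same planned follow-up and are unaffected, and the overall column moves little. This is a reporting weakness in primary-objective tables, worth correcting because the remedy is cheap.

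**What to change.** Keep the crude percentages. For overall TEAEs, TESAEs, each AESI and MACE, by feeder group and overall, add subjects with a first event per 100 subject-years at risk, with 95% CI.

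- **Time at risk.** Run it from ORION-8 baseline to the earlier of first event or EOS, with the same end applied to events and to time. Protocol 8.4.2 and 10.2.3 put that end at EOS; the SAP's TEAE rule states none and should.
- **Denominator.** Do not reuse SAP 2.4.1 exposure, mainly because it does not stop at the first event.
- **Footnotes.** State the shorter ORION-3 follow-up. State also that the rate corrects for length of follow-up only, not for differences in feeder population or prior exposure, and that it assumes a roughly constant hazard.

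Optionally, report injection-site TEAEs per inclisiran injection and show events after the Day 1 placebo injection separately. Scheduled inclisiran injections differ by column: 6 (plus one placebo) for Inclisiran-Inclisiran, 7 for Placebo-Inclisiran, and 5, 4 or 3 for ORION-3 at EOS Day 900, 720 or 540.

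The cost is one time-at-risk derivation per listed category from onset dates already collected, some added columns, and a second incidence measure to explain. The tables by system organ class and preferred term can stay as planned.

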### **2.7.1.1 AEs of special interest (AESI) and additional safety topics**

#### **2.7.1.1.1 AEs at the injection site**

TEAEs at the injection site, which is an AESI, include all TEAEs identified as being an AE at the injection site on the AE page of eCRF or with “injection site reactions” as the high-level term (HLT).

The number of injection site TEAEs per subject will be summarized using descriptive statistics as well as the number of subjects with 0, 1, 2, 3, ... injection site TEAEs.

The following summaries will be presented for ORION-8 injection site TEAEs using number and percentage of subjects with the event:

- Overall Summary of TEAEs
- TEAEs by PT
- TEAEs by PT and maximum severity

- TESAEs by PT
- Signs and symptoms of TEAEs (only applicable to the events identified as AEs at the injection site on eCRF)
- TEAEs by PT and worst outcome

Outcomes of TEAEs ordered from worst to best will be:

- 1) Fatal
- 2) Not resolved
- 3) Resolved with sequelae
- 4) Unknown
- 5) Resolving
- 6) Resolved

For subjects whose injection site TEAEs are all resolved (i.e. the worst outcome for the subject is “Resolved”), the duration (in days) of injection site TEAEs will be summarized using descriptive statistics. If a subject has multiple durations, the median time will be used for that subject.

A subject data listing will be provided for injection site AEs. Such listing will include all AEs in ORION-8 database, regardless of whether they are ORION-8 TEAE.

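### An injection-site reaction that worsens is counted as two or three events, and its duration is either split or dropped, because the SAP has no rule to join records of one reaction

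*SAP*

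**What the plan says.** SAP 2.7.1 describes how worsening is recorded: "the investigators are required to enter any worsened AE as a separate record". It draws the operational consequence that "implementation-wise an AE is a TEAE as long as its onset date/time" is on or after ORION-8 baseline. Treatment emergence is thus decided one record at a time.

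For injection-site events, which are an AESI, SAP 2.7.1.1.1 plans two summaries that go beyond counting subjects:

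- **Events.** "The number of injection site TEAEs per subject will be summarized using descriptive statistics", together with the distribution of subjects having 0, 1, 2, 3 or more such events.
- **Duration.** The restriction is "For subjects whose injection site TEAEs are all resolved"; in those subjects "the duration (in days) of injection site TEAEs will be summarized using descriptive statistics". Then: "If a subject has multiple durations, the median time will be used for that subject".

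The same section tabulates worst outcome by preferred term. It ranks *Not resolved* second worst and *Resolved* best, with *Resolved with sequelae*, *Unknown* and *Resolving* between them.

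The one de-duplication rule is in SAP 2.7.1: with repeated events under the same term, "the subject will be counted only once for that SOC/PT". It governs tables of subjects with an event. It does not reach event counts or durations. Neither document links records that belong to one reaction, defines the start and stop of a duration, or says how the earlier record is closed when an event worsens.

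**The concern.** The recording rule makes the record the unit, while a reader will take the summaries in SAP 2.7.1.1.1 to describe reactions. A single reaction going from mild to moderate produces two treatment-emergent records.

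In the 0/1/2/3 table, a subject with one worsening reaction then looks the same as a subject who reacted to two separate injections. That difference matters here. Protocol Table 6-1 schedules up to seven injections for subjects from the Phase III feeder studies (Day 1, Day 90 and five later dosing visits), and whether reactions recur is a natural question for long-term tolerability.

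Long-term safety and tolerability is a primary objective (Protocol 2.1), and Protocol 1.3 names injection-site reaction as the only event so far ascribed to inclisiran. The reactions misdescribed are the ones that got worse.

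**Working it through.** The documents give no figure on this point, so there is none to reproduce. The check applies the SAP's rules to worked cases.

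**Inputs**

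- Separate record per worsening, and treatment emergence by record onset: SAP 2.7.1.
- Event count, within-subject median, all-resolved restriction and outcome ranking: SAP 2.7.1.1.1.
- Three severity grades: Protocol 8.2.1.
- Reactions in about 5% of subjects in ORION-1: Protocol 1.2.2.2.2. Carrying this over to ORION-8 is an assumption, made for scale only.
- 2991 subjects enrolled: Protocol, Amendment 2.
- Share *q* of reactions that worsen once: not in the documents. Assumed range 10–30%.

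**Step 1: events per reaction.** Records = 1 + number of worsenings. One worsening gives 1 + 1 = 2. Mild to moderate to severe gives 1 + 2 = 3.

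**Step 2: mean events per subject.** Let *p* be the share of subjects with a reaction, one reaction each. The mean over all subjects is *p*(1 + *q*).

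| *q* | Mean among subjects with a reaction | Mean over all subjects (*p* = 0.05) |
|---|---|---|
| 0 | 1.00 | 0.050 |
| 0.10 | 1.10 | 0.055 |
| 0.30 | 1.30 | 0.065 |

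In subjects: 0.05 × 2991 ≈ 150 with a reaction, of whom 15 (10%) to 45 (30%) would appear under 2 events instead of 1.

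**Step 3: duration if the earlier record is closed as *Resolved*.** A reaction of *D* days that worsens after *w* days gives records of *w* and *D* − *w*. The median of two values is their mean, so the subject's duration is *D*/2 whatever *w* is:

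- 2 + 4 days: median 3, true length 6.
- 2.5 + 7.5 days: median 5, true length 10.
- Two 10-day reactions, one worsening midway: median(10, 5, 5) = 5, against median(10, 10) = 10.

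If both end days are counted and the two records share a day, the first two results move by half a day; hence about half. Among subjects with one reaction each, and if worsening reactions last as long on average as the others, the mean duration is multiplied by 1 − *q*/2, which is 0.95 to 0.85.

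**Step 4: duration if the earlier record is closed under any other code.** Not all of the subject's events are then *Resolved*, so the subject leaves the duration summary. Nothing is shortened, but 10–30% of subjects with one reaction are removed, and they are exactly those whose reaction worsened. If the code is *Not resolved*, that becomes the subject's worst outcome even though the reaction later resolved.

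**Step 5: what does not move.** Subjects with an event by preferred term, by maximum severity and for serious events are counted once, so an additional record of the same reaction under the same term changes nothing.

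**The case against.** The strongest case against has four parts.

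1. **The SAP sentence on worsening serves another purpose.** It explains how treatment emergence relative to ORION-8 baseline is programmed; it does not set out to define an event for counting. Protocol 8.3.2 also sends injection-site reactions to dedicated eCRF pages, which are not part of the documents, so the recording detail may differ. This limits certainty about the mechanism but does not remove it: the SAP rule covers any worsened event, and SAP 2.7.1.1.1 itself identifies injection-site events from the AE page.

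2. **Durations.** A reader might infer that durations are halved as a matter of course, and that this is independent of the restriction to resolved events. The documents support neither. They do not say that durations are computed per record or how the earlier record is closed. Halving needs a code of *Resolved* on a reaction that is still present and worsening. Under any other code the restriction itself decides the result, by exclusion. This part of the objection stands.

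3. **Size.** A reader might take a 10–30% inflation of event frequency as established. No worsening rate is given. Protocol 1.2.2.2.1 and 1.2.2.2.2 describe reactions as infrequent, mild to moderate and short-lived, and the absolute change is 0.005 to 0.015 events per subject. This stands.

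4. **The main tables are protected.** The subject-level incidence tables are sound, every injection-site event is listed, and counting each change of severity is a possible convention. All true, but the SAP does not say that it has adopted that convention.

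**Conclusion.** The point holds for event counts. Following the plan as written, one reaction that worsens becomes two or three injection-site events, and no rule in either document prevents it. For durations it holds conditionally: the summary misdescribes worsened reactions either way, by roughly halving them or by excluding them, and the plan does not say which.

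The impact is small. With the assumed 5% of subjects having one reaction and 10–30% of reactions worsening once, the mean per subject rises from 0.050 to between 0.055 and 0.065. No hypothesis test, sample size or primary efficacy result depends on it. It is worth correcting because it concerns a primary-objective safety summary of the one event ascribed to the drug, and the correction is cheap.

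**What to change.** In SAP 2.7.1.1.1, before counting events and deriving durations and worst outcome, collapse contiguous injection-site TEAE records of the same subject and preferred term, with no injection in between, into one episode. Prespecify the permitted gap; at most 1 day is an example and is not taken from the documents. The episode runs from first onset to final resolution and carries the maximum severity and the final outcome. Merge only records already classed as TEAEs, so that the worsening of a pre-baseline reaction remains treatment-emergent.

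The least that would do is to label both summaries as record-level and state how the earlier record is closed, with which end date and outcome, when a reaction worsens.

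The cost is a short derivation and no new data. The mean count, the table of subjects with 0, 1, 2, 3 or more events, the duration summary and possibly the worst-outcome table will change. A worsening coded to a different preferred term would still not be merged; the SAP should state that limitation.
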